5.3 OTHER

Not applicable

5.4 APPROPRIATENESS OF MEASUREMENTS

The measures conducted within this Registry Program reflect the current real-world approach regarding clinical practice across the different countries.

Proprietary confidential information.

© 2014 Boehringer Ingelheim International GmbH or one or more of its affiliated companies. All rights reserved.

This document may not - in full or in part - be passed on, reproduced, published or otherwise used without prior written permission.

6. INVESTIGATIONAL PLAN

6.1 VISIT SCHEDULE

Recommended timing of assessments is presented in the Flow Charts for Phases II and III of the Registry Program, and summarized in [Table 6.1: 1](#). The time intervals given for each of the scheduled visits serve as indicators as to when the contact to the patient as well as the respective data entry into the registry data base (eCRF) should take place. All assessments are intended to be performed during one visit (cf. [Flow Chart](#)), e.g. at the time of a routine, scheduled appointment. The information from each visit should be entered as quickly as possible into the eCRF after patient contact and may only be delayed in case medical record abstraction is required e.g. to capture INR data, which may not be immediately available if not performed at the site.

Due to the observational design, the dates for follow-up visits are only recommendations. The visit windows allow for flexibility. Collection of data in the study should be managed during routine practice visits (i.e., the visits should not be conducted via telephone.). In the exceptional case that a physical visit is not possible e.g. due to the transient inability of a patient to attend the practice, this particular visit can be conducted via telephone with the patient. However, all efforts should be made to ensure that the following visit is again a physical visit.

The sites selected for participation in the study are invited to all phases of the Registry Program described in the present protocol. However, additional sites may be opened to accelerate recruitment for Phase II or Phase III. The site staff will be asked to provide data regarding site and physician characteristics, including:

- type of facility (e.g. general practice, specialist office, community hospital, university hospital, out-patient care center, anti-coagulation clinic)
- specialty of the treating physician/investigator
- size of clinic/practice
- numbers of newly diagnosed AF patients during last 12 months

Table 6.1: 1 Schedule of data collection* (cf. [Flow Chart](#))

| | Baseline | 3 months (± 1 month) | 6 months (± 1 month) | 12 months (± 2 month) | 24 months (± 2 month) | 36 months (± 2 month) |
|-------------|----------|-------------------------|-------------------------|--------------------------|--------------------------|--------------------------|
| Phase II** | X | X [§] | X [§] | X [§] | X [§] | - |
| Phase III** | X | - | X | X | X | X |

* Due to the observational design, the dates for follow-up visits are only recommendations. Visit windows allow for flexibility. Collection of data in the study should be managed during routine practice visits

**Patients will take part either in Phase II or in Phase III

§ Follow-up in patients prescribed dabigatran (at baseline) only

Proprietary confidential information.

© 2014 Boehringer Ingelheim International GmbH or one or more of its affiliated companies. All rights reserved.

This document may not - in full or in part - be passed on, reproduced, published or otherwise used without prior written permission.

6.2 DETAILS OF STUDY PROCEDURES AT SELECTED VISITS

6.2.1 Assessments in Phase II of GLORIA-AF

The following data will be collected for all patients in Phase II at enrollment, for the purposes of cross-sectional analyses. Follow-up assessments will be done only in patients who receive dabigatran. The baseline visit is defined as the physical visit when the patient is enrolled in the registry.

Assessments at Baseline:

- Date of baseline visit
- Date of informed consent
- Date of diagnosis of non-valvular AF
- Inclusion/exclusion criteria
- Demographic data, including: date of birth (month and year), gender, weight, height (calculated BMI) and race
- Blood pressure, heart rate and serum creatinine (if available)
- Information regarding AF
 - Symptomatic, minimally symptomatic, asymptomatic
 - Type (paroxysmal, persistent, permanent)
 - Previous cardioversion, ablation, pacemaker, implantation, use of LAA occlusion device and/or left atrial procedures
- Medical history (including current concomitant diseases)
- Selected concomitant treatments (antihypertensive, heart failure and anti-arrhythmic therapies, metabolic and anti-inflammatory) and other selected drugs.
- Antithrombotic treatment selected including start date (all antithrombotic therapies, for stroke prevention as well as other indications).

Assessments at the Follow-up Visits (cf. [Flow Chart](#)):

- Date of follow up visit
- Type of follow up visit
- Concomitant diseases (current, any change)
- Serum creatinine to be recorded (if available)
- Antithrombotic treatment (current, any change (start and stop dates) including compliance, reason for change; including interruptions of antithrombotic treatment due to therapeutic/diagnostic interventions)
- Selected concomitant treatment (current, any change)
- Outcome events as listed in [Section 5.1](#)
- Information is recorded on any therapeutic/diagnostic interventions that occur as part of regular follow-up
- All serious adverse events judged as related or unrelated to any BI drug (see [section 5.2.2.2](#))
- Non-serious adverse events judged as related to any antithrombotic therapy including dabigatran or to any BI drug (see [section 5.2.2.2](#))

Proprietary confidential information.

© 2014 Boehringer Ingelheim International GmbH or one or more of its affiliated companies. All rights reserved.

This document may not - in full or in part - be passed on, reproduced, published or otherwise used without prior written permission.

- Vital status (only at last follow-up visit)

Only for those patients who are prescribed dabigatran the 3-, 6-month, 12-month (1 year) and 24 months (2 year) follow-up visits should be conducted. All follow-up visits and assessments should be conducted even if the patient discontinues treatment with dabigatran or switches to another antithrombotic treatment for AF.

If a patient prematurely discontinues from the registry, a follow-up assessment should be performed at time of study discontinuation if possible, and the end of study eCRF completed.

6.2.2 Assessments in Phase III of GLORIA-AF

In Phase III a baseline assessment is performed for all patients, identical to the baseline assessments for Phase II as described in Section [6.2.1](#).

Follow-up assessments will be done for ALL patients (i.e. irrespective of antithrombotic treatment status).

Assessments at Follow-up Visits:

Follow-up visits: 6-month, 12-months (1 year), 24-months (2 years) and 36-months (3 years) after Baseline visit.

- Date of follow-up visit
- Type of follow-up visit
- Concomitant diseases (current, any changes)
- Serum creatinine to be recorded (if available)
- Antithrombotic treatment (current, any change (start and stop dates) including compliance, reason for change; including interruptions of antithrombotic treatment due to therapeutic/diagnostic interventions)
- Selected concomitant treatment (current, any change)
- Patients receiving VKAs: the last three INR values and dates performed, from files and if necessary by contacting INR clinics, hospitals, etc.
- Information about VKA therapy such as location of INR testing (physician's office, freestanding lab, home testing), including discontinuations and re-starts, dates, reasons for changes, etc.
- Outcome events as listed in [Section 5.1](#)
- Information is recorded on any therapeutic/diagnostic interventions that occur as part of regular follow-up
- All serious adverse events judged as related or unrelated to any drug (see [section 5.2.2.2](#))
- Non-serious adverse events judged as related to any antithrombotic therapy including dabigatran, or to any BI drug (see [section 5.2.2.2](#))
- Vital status (only at last follow-up visit)

If a patient prematurely discontinues from the registry, a follow-up assessment should be performed at time of study discontinuation if possible, and the end of study eCRF completed.

Proprietary confidential information.

© 2014 Boehringer Ingelheim International GmbH or one or more of its affiliated companies. All rights reserved.

This document may not - in full or in part - be passed on, reproduced, published or otherwise used without prior written permission.

6.2.3 End of study and follow-up period

For early Discontinuation:

- Date of Registry discontinuation
- Reason for Registry discontinuation
- Vital status

Proprietary confidential information.

© 2014 Boehringer Ingelheim International GmbH or one or more of its affiliated companies. All rights reserved.

This document may not - in full or in part - be passed on, reproduced, published or otherwise used without prior written permission.

7. STATISTICAL METHODS AND DETERMINATION OF SAMPLE SIZE

Details of all analyses will be provided in the statistical and epidemiological analysis plan (SEAP).

7.1 STATISTICAL DESIGN - MODEL

Phase II and III of this prospective, multi-center observational study consist of a cross-sectional collection of baseline data for newly diagnosed non-valvular AF patients and a two and three years follow-up period, respectively. Within Phase II only patients who receive dabigatran for AF treatment at baseline will be followed longitudinally. Within Phase III all patients will be followed longitudinally and the groups of newly diagnosed AF patients started on VKA and dabigatran, respectively, are assumed to be comparable in terms of important baseline characteristics due to the design of the Registry Program.

The newly diagnosed non-valvular AF population will be described using a cross-sectional approach.

For Phase II, longitudinal data on dabigatran treated patients will be summarized descriptively.

In Phase III, given that initiators of dabigatran and VKAs are comparable regarding important baseline covariates, the comparison between dabigatran and VKAs in terms of the composite endpoint in Phase III will be based on multivariable regression models using time-to-event methodology. However, if comparability of baseline characteristics is insufficient, alternative approaches will be followed to assess long-term outcomes ([see section 3.1](#)).

Due to the variable time at risk in this registry setting, analysis of outcome events will focus on incidence rates and cumulative risk using Kaplan-Meier curves or other life-table techniques.

7.2 NULL AND ALTERNATIVE HYPOTHESES

There is no (confirmatory) hypotheses testing foreseen in a strict statistical sense.

However, the main and further objectives are defined in [Section 2](#). Additional research objectives can be described in the SEAP.

7.3 PLANNED ANALYSES

Analyses will be performed by Boehringer Ingelheim or Boehringer Ingelheim's designees.

A final analysis and a report of Phase II will be prepared once the data collection of Phase II is completed, the data are cleaned and the database is locked. The final analysis of Phase III

Proprietary confidential information.

© 2014 Boehringer Ingelheim International GmbH or one or more of its affiliated companies. All rights reserved.

This document may not - in full or in part - be passed on, reproduced, published or otherwise used without prior written permission.

(if conducted) will be done after Phase III is completed, the data are cleaned and the database is locked. It will be described in a combined report of Phases II and III together.

Analyses on a country level might be performed in addition, once the report or interim report of phase II (or phase III) is available or if required due to regulatory requirements.

The main analysis population will consist of all eligible patients (i.e. all patients fulfilling all inclusion criteria and no exclusion criteria) and the analysis will focus on the antithrombotic treatment choice for stroke prevention at baseline.

Summary statistics for continuous variables will include the N, mean, standard deviation, minimum, Q1 (lower quartile), median, Q2 (upper quartile), and maximum value; tabulations of categorical variables will present all possible categories and will display the number of observations per category as well as percentages. All estimates will be presented with 95% confidence intervals.

Additionally, similar primary and other analyses as described for the total Registry Program also will be conducted using data from only patients enrolled in the EU/EEA member states covered by this protocol (1160.136).

7.3.1 Main analyses

A) Patient characteristics influencing choice of antithrombotic treatment for stroke prevention at baseline

Demographics and baseline characteristics (including specifically stroke/bleeding risk scores (CHADS₂, CHA₂DS₂-VASc and HAS-BLED, see [Appendix 10.1](#))) will be summarized descriptively for all eligible patients by antithrombotic treatment choice for stroke prevention at the baseline visit.

The antithrombotic treatment choice for stroke prevention at the baseline visit (e.g. none, VKAs, ASA, clopidogrel, dabigatran, etc.) will be described.

Potential channeling bias between patients initiating dabigatran and VKA at the patient's baseline visit will be explored using comparisons of important baseline characteristics (known risk factors for stroke and bleeding, e.g. age, gender, hypertension, diabetes mellitus, prior stroke, prior transient ischemic attack, prior bleeding and concomitant medication use) between the two groups at regular intervals during Phase II and Phase III. This includes the generation of two-way comparisons for each of the baseline characteristics (dabigatran versus VKA) and calculation of a propensity score using multiple regression models to predict the probability of treatment choices (see also interim analyses [7.3.4](#)).

B) Important outcome events (Phase II only)

Incidence rates and cumulative risks over time since initiation with 95%-confidence intervals for important outcome events (see [Section 5.1](#).) will be calculated within the dabigatran cohort. In addition these analyses will be done stratified by chronic antiplatelet treatment at baseline. The analysis will be based on all eligible patients initiating dabigatran for stroke

Proprietary confidential information.

© 2014 Boehringer Ingelheim International GmbH or one or more of its affiliated companies. All rights reserved.

This document may not - in full or in part - be passed on, reproduced, published or otherwise used without prior written permission.

prevention at baseline. Patients who discontinue initial dabigatran treatment for stroke prevention permanently will be censored at date of last drug intake + 3 days or at first intake of other relevant chronic antithrombotic treatment for stroke prevention, whatever comes first (unless the event occurred prior to the time of censoring). A patient is considered to have permanently stopped initial dabigatran treatment if other relevant chronic antithrombotic treatment is initiated for stroke prevention or otherwise dependent on the duration of a treatment interruption (thresholds of treatment interruption duration and other details will be described in the SEAP).

C) Important outcome events / analysis of composite endpoint of stroke, SEE, vascular death, MI, life-threatening bleeds (Phase III only)

Incidence rates and cumulative risks with 95%-confidence intervals for the composite endpoint and for the individual components of the composite endpoint will be calculated. This analysis will be repeated within subgroups. Examples of subgroup variables are age, gender and stroke and bleeding risk factors. In addition the calculation of incidence rates and cumulative risks will be done stratified by chronic antiplatelet treatment. If the patients initiating dabigatran treatment for stroke prevention at baseline are comparable (in terms of important baseline characteristics) to those initiating VKA treatment, incidence rates within these two groups will also be reported.

The analysis will be based on antithrombotic treatment choice prescribed for stroke prevention at baseline and all eligible patients. Patients who discontinue initial antithrombotic treatment for stroke prevention permanently will be censored at date of last drug intake + 3 days (for dabigatran and non VKA treatments) and +6 days (for VKA treatment or combinations of VKA with other antithrombotic treatments) or at first intake of other relevant chronic antithrombotic treatment for stroke prevention, whatever comes first (unless the event occurred prior to the time of censoring). A patient is considered to have permanently stopped initial antithrombotic treatment for stroke prevention, if other relevant chronic antithrombotic treatment is initiated for stroke prevention or otherwise dependent on the duration of treatment interruption (details will be described in the SEAP).

Proprietary confidential information.

7.3.3 Safety analyses

The safety analysis will include all patients enrolled in Phase II and Phase III with planned follow up (i.e. only patients starting on dabigatran in phase II). Statistical analysis and reporting of AEs will be descriptive in nature, will be based on BI standards and will focus on adverse drug reactions (related to antithrombotic therapy for stroke prevention). No hypothesis testing is planned.

Occurrences of AEs will be analyzed relative to the number of patients treated and additionally relative to observed patient-years (i.e. time at risk). The safety analysis will be based on the concept of treatment emergent adverse events. Patients will be analyzed according to the antithrombotic treatment for stroke prevention they have received at the time of the event. If no current antithrombotic treatment for stroke prevention is administered then events occurring within a washout period of three days (in case of dabigatran and non VKA treatments) or six days (in case of VKA treatment or combination of VKA with other antithrombotic treatment) after discontinuation of antithrombotic treatment will be assigned to the last treatment given. This washout period will also be included as time at risk for derivation of total patient-years. Adverse events that deteriorate under treatment will also be considered as 'treatment emergent'. Adverse events occurring prior to first intake of antithrombotic treatment for stroke prevention prescribed at baseline, during periods without any antithrombotic treatment (excluding washout period) or after the individual 2 year (Phase II) or 3 year (Phase III) follow-up visit dates (excluding washout periods) will not be considered treatment emergent events and will not be included in summary tables.

The safety analyses will include the following parameters:

- ADRs (related to antithrombotic therapy for stroke prevention)
- ADRs (related to antithrombotic therapy for stroke prevention) leading to discontinuation of antithrombotic treatment
- Serious ADRs (related to antithrombotic therapy for stroke prevention)
- Deaths
- SAEs

Additionally, an analysis of ADRs restricted to those events which are related to the antithrombotic treatment for stroke prevention initiated at baseline will be performed.

Systematic collection of vital signs and laboratory parameters is not planned.

Proprietary confidential information.

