| Name of active ingredient: Dabigatran (dabigatran etexilate = prodrug) | | | |
| Protocol date: 23 March 2012 | Trial number: 1160.136 | | Revision date: 22 October 2014 |
| No. of patients: | For the EU/EEA* member states, enrollment of approximately 5,000 patients in Phase II and another 10,000 patients in Phase III is planned in total. | | |
| Diagnosis: | Patients newly diagnosed with non-valvular atrial fibrillation | | |
| Main criteria for inclusion: | Patients newly diagnosed with non-valvular atrial fibrillation (diagnosed < 3 months before patient's baseline visit) and at risk for stroke (CHA ₂ DS ₂ -VASc score of at least 1), aged 18 years or older. | | |
| Duration of follow up: | 2 years for patients initiating dabigatran (Phase II); 3 years for all patients (Phase III) irrespective of anticoagulation treatment status | | |
| Outcomes: | Collect data on patient demographics, AF disease information, antithrombotic treatment, medical history and concomitant medication at the patient's baseline visit. In addition, compliance with the dabigatran SmPC will be examined. The patients will be followed for 2 (Phase II) and 3 years (Phase III) respectively and information such as change in antithrombotic medication since previous visit including compliance and occurrence of any outcome or safety events will be captured. In Phase II follow-up information will be collected for those patients initiating dabigatran, in Phase III for all patients. | | |
| Criteria for safety: | SAEs, ADRs and major and life threatening bleeds | | |
| Statistical methods: | Descriptive statistics for patient characteristics and treatment patterns, multivariable regression models for analyzing predictors of outcomes and for comparative analyses | | |
| * European Union/European Economic Area | | | |

Proprietary confidential information.

© 2014 Boehringer Ingelheim International GmbH or one or more of its affiliated companies. All rights reserved.

This document may not - in full or in part - be passed on, reproduced, published or otherwise used without prior written permission.

FLOW CHART**OVERVIEW**

| Phase of registry | Baseline (time point of start of observation) | Time point 1 3 months from baseline (only phase II) | Time point 2 6 months from baseline | Time point 3 12 months from baseline | Time point 4 24 months from baseline | Time point 5 36 months from baseline |
|-------------------|--|---|--|---|---|---|
| II* | V-B | V1§ | V2§ | V3§ | V4§ | |

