| Description of change | | Added to Flow Chart Phase II and Phase III, information if available on serum creatinine and any therapeutic/ diagnostic interventions. Clarify Non-Serious Adverse Event Reporting in Phase II to match that of phase III. Any Non-Serious Adverse events related to any antithrombotic use will now be recorded on eCRFs in Phase II as |

Proprietary confidential information.

© 2014 Boehringer Ingelheim International GmbH or one or more of its affiliated companies. All rights reserved.

This document may not - in full or in part - be passed on, reproduced, published or otherwise used without prior written permission.

| | | |
|-----------------------------------|--|---|
| Number of global amendment | | 1 |
| | | well as Phase III. |
| Rationale for change | | Include serum creatinine and therapeutic/diagnostic interventions. Clarify and streamline Non-Serious Adverse Event reporting. |
| Section changed #4 | | 1.1 Medical Background |
| Description of change | | Clarify countries where dabigatran has been approved. |
| Rationale for change | | Section required updating. |
| Section changed #5 | | 3.1 Overall Design and Plan |
| Description of change | | Add substudy 1160.171 to be conducted in India. Add that interim analyses will occur on a regional basis based on the number of patients enrolled (approximately once or twice a year). |
| Rationale for change | | India was added as part of a separate substudy (1160.171) for administrative and logistical reasons only. Timing of interim analysis was formerly approximately every 6 months, but the timing of analysis is more driven by adequate number of patients enrolled. |
| Section changed #6 | | 3.1 Overall Design and Plan |
| Description of change | | Clarify planned number of countries, sites and patients in the EU. Clarify planned registry period will be from July 2011 to June 2020. Enrollment will end after the overall enrollment goal has been met, or by June 2017, whichever comes first. |
| Rationale for change | | Clarification of registry period and to indicate possibility for some regions to end early. |
| Section changed #7 | | 3.2 Discussion Of Study Design, Including The Choice Of Control Group(s) |

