| Description of change | | "Fatal bleeding" removed from "Major bleeding, defined as meeting one or more of the following criteria" and placed under "Life-threatening bleeding, as defined as meeting one or more of the following criteria". |
| Rationale for change | | Clarification |
| Section changed #13 | | 5.2.2.1 Assessment of Adverse Events |
| Description of change | | Added section on 'Worsening of Pre-existing Conditions' |
| Rationale for change | | Added to be in conformance to the drug safety SOP 001-MCC-40-002 |
| Section changed #14 | | 5.2.2.2 Assessment of Adverse Events AE reporting instructions were clarified and addition of an always serious list was added. |
| Description of change | | Inclusion of BI list of AEs which are defined to be always serious. This means that these events are, by their very nature, always defined as serious even if an occurrence of one of these events does not technically meet the usual criteria for seriousness (for example, stroke). Unified instructions for AE reporting for Phases II and III. It was determined that it was not necessary to have separate instructions for Phase II and III. The only change is clarification that the requirement to report non-serious AEs which are deemed related to an antithrombotic other than dabigatran applies to both Phase II and III. Further clarification is provided to the investigator about what reporting functions are performed automatically by the system and what are the responsibilities of the site personnel. It is also clarified that Non-serious AEs which are deemed related to a BI drug must be reported to BI within seven days of the site learning of the AE. |
| Rationale for change | | Streamlined and simplified instructions for |

Proprietary confidential information.

© 2014 Boehringer Ingelheim International GmbH or one or more of its affiliated companies. All rights reserved.

This document may not - in full or in part - be passed on, reproduced, published or otherwise used without prior written permission.

| | | |
|-----------------------------------|--|---|
| Number of global amendment | | 1 |
| | | reporting of SAEs and non-serious AE and required reporting timeline for NSAE reporting of related events was clarified. |
| Section changed #15 | | 6.1 Visit Schedule and Table 6.1: 1 Schedule of data collection |

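### Phase II rates of non-serious reactions to antithrombotics other than dabigatran are probably understated, because recording of those reactions appears to start only with amendment 1 while Protocol 7.3.3 counts all patient-years on those drugs

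*Protocol*

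**What the plan says.** **Follow-up after a switch.** In Phase II only dabigatran starters are followed, but Protocol 6.2.1 keeps them in follow-up whatever happens to the drug: "All follow-up visits and assessments should be conducted even if the patient discontinues treatment with dabigatran or switches to another antithrombotic treatment for AF".

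**Numerator and denominator.** Protocol 7.3.3 assigns events to the drug in use: "Patients will be analyzed according to the antithrombotic treatment for stroke prevention they have received at the time of the event". On the denominator it says: "Occurrences of AEs will be analyzed relative to the number of patients treated and additionally relative to observed patient-years". The listed outputs include ADRs related to any antithrombotic for stroke prevention, serious or not. Nothing in 7.3.3 restricts events or time by calendar date or protocol version.

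**Change in recording.** The summary of changes after Appendix 10.3 describes the move from version 3 (23 March 2012) to the current text ("Revision date: 22 October 2014"). Its item 3 says: "Any Non-Serious Adverse events related to any antithrombotic use will now be recorded on eCRFs in Phase II", bringing Phase II into line with Phase III. Its item 14 adds: "It was determined that it was not necessary to have separate instructions for Phase II and III". The same item also says: "The only change is clarification that the requirement to report non-serious AEs which are deemed related to an antithrombotic other than dabigatran applies" to both phases. The amendment was to be put into effect only after ethics committee or authority approval.

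**Where the detail sits.** The SAP covers Phase III and refers the Phase II analyses to a separate document, which is not available here.

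**The concern.** A rate is interpretable only if the events in its numerator could have been recorded throughout the time in its denominator. Here the denominator for a non-dabigatran drug in Phase II is all time on that drug after a switch. If sites were not asked to record non-serious reactions to that drug before amendment 1, the earlier part of this time could contribute no such events.

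The bias runs one way: the other antithrombotics look better tolerated in Phase II than they were. Percentages of patients treated are affected as well as rates per patient-year. Section 7.3.3 says the safety analysis will focus on ADRs, so this touches a main safety output.

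The summary of changes is used only to date the recording rule. A difference between it and the current text is not itself the issue. The issue is that current 7.3.3 combines time collected under two recording rules.

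**Working it through.** **1. Reproduce the plan's figure.** Protocol 7.6 gives 2,500 dabigatran starters, 2 years of follow-up and 25% per year for discontinuation plus loss to follow-up. With λ = −ln(0.75):

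- On-drug patient-years = 2,500 × (1 − 0.75²)/λ = 3,802, as stated.
- The same formula with 2,000 patients and 3 years gives 4,019, also as stated for Phase III.

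**2. Ceiling on off-index time.** 2,500 × 2 − 3,802 = 1,198 patient-years. This includes untreated time and time lost to follow-up, so time on another antithrombotic is smaller by an amount the documents do not give.

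**3. Share of off-index time before the amendment took effect.** Per patient, expected off-index time up to u years after entry is G(u) = u − (1 − 0.75^u)/λ. G(2) = 0.479, and 2,500 × 0.479 = 1,198. For entry date e and effective date C, the share is the average of G(min(2, max(0, C − e))) over entry dates, divided by G(2). Phase II enrolment dates are not stated. The windows below are assumptions, with uniform entry and C at 22 October 2014 plus 0 or 6 months.

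| Assumed entry window | No delay | 6 months' delay |
|---|---|---|
| 2012.25 to 2013.5 | 84% | 99% |
| 2012.25 to 2014.0 | 69% | 89% |
| 2012.25 to 2014.8 | 49% | 68% |
| 2012.25 to 2015.5 | 39% | 54% |
| 2013.0 to 2014.8 | 29% | 55% |
| 2013.0 to 2015.5 | 21% | 40% |

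The range is 21% to 99%.

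**4. Effect on the rates.** Let f be the share of patient-years on other antithrombotics before the amendment took effect, and s the non-serious share of ADRs. With a constant rate and no later back-entry, recorded/true is 1 − f for non-serious ADRs and 1 − f·s for all ADRs. Neither f nor s is in the documents. For all ADRs:

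| f | s = 0.5 | s = 0.75 | s = 1 |
|---|---|---|---|
| 0.25 | 0.88 | 0.81 | 0.75 |
| 0.50 | 0.75 | 0.63 | 0.50 |
| 0.75 | 0.63 | 0.44 | 0.25 |

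Over this grid the shortfall is 12.5% to 75%. Counting events and time only after the amendment took effect returns the ratio to 1. With f = 0.5 that leaves at most 1,198 × 0.5 = 599 patient-years.

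**5. What is not affected.** Protocol 5.2.2.2 collects all SAEs and outcome events regardless of cause, so serious ADRs and deaths stand. The additional ADR analysis restricted to the drug started at baseline concerns dabigatran in followed Phase II patients. The SAP tables are Phase III only.

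**The case against.** **The version 3 rule is not available.** The summary of changes is mixed. Its repeated use of clarification for an existing requirement could mean that sites already had the duty. This stands as a reason to confirm the rule, and a reader should not take it as established that recording began with the amendment. It does not remove the point. Item 3 says such events will now be recorded, item 14 says separate instructions were merged, and the same summary labels substantive edits as clarification (items 11 and 12, on outcome measures and fatal bleeding).

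**The Phase II analysis plan may already handle this.** Possible, and it cannot be checked. Protocol 7.3.3 as written gives no such rule.

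**Reactions before the amendment may have been entered later.** Events are gathered at visits up to a year apart, and the seven-day limit for non-serious reactions applies to the sponsor's drugs. A visit after implementation could pick up earlier reactions. Back-entry is neither required nor excluded, so the shares in step 3 are upper-end figures for the understatement.

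**No comparison is planned.** Phase II longitudinal data and AEs are descriptive, with no hypothesis testing. A reader might infer that pooled Phase II and III tables will make dabigatran look worse tolerated. The documents do not support that: 7.3.3 includes both phases and 7.3 foresees a combined report, but no available passage plans pooled ADR rates.

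**The dabigatran column is not wholly clean.** A reader might also infer that the dabigatran column is unaffected. Under the same reading of the summary of changes, non-serious reactions attributed only to a co-administered antithrombotic, such as ASA, during dabigatran treatment would also have gone unrecorded.

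**Conclusion.** The concern holds in a limited form. If Phase II recording of non-serious reactions to other antithrombotics began with amendment 1, as the summary of changes indicates, then 7.3.3 as written understates the Phase II rates of non-serious ADRs, and so of all ADRs, on non-dabigatran drugs after a switch. The direction follows from the text.

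The size does not. At most 1,198 patient-years are involved, and the 21% to 99% rests on assumed entry windows, uniform entry, exponential discontinuation and a delay of 0 to 6 months. Earlier entry or later local approval would raise the share; back-entry would lower the bias.

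It should be corrected before Phase II ADR tables by treatment at the time of the event are produced. It does not call into question the serious-event, outcome or Phase III results.

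**What to change.** - Confirm from version 3 and the site instructions what Phase II sites were asked to record before amendment 1.
- In 7.3.3 and the Phase II analysis, choose one rule for the Phase II columns of non-dabigatran antithrombotics. Either report only serious ADRs and SAEs there, or count non-serious ADRs and their patient-years only from the date the amendment took effect, by site or country approval date.
- Footnote the Phase II dabigatran column to say that non-serious reactions attributed only to a co-administered antithrombotic may be missing before that date.
- Take any between-treatment comparison of non-serious ADR rates from Phase III only.

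**Cost.** A short rule in the analysis text and a footnote. Under the second option, approval dates must also be added to the programming for up to about 680 sites in up to 23 countries (country-level dates would be lighter), and fewer Phase II patient-years remain on other antithrombotics. The first option needs no dates but gives up the non-serious events for those drugs in Phase II. No new patient data are needed.
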